#### **4.3 Recruitment**

Pregnant women at  $\geq 26$  weeks 0 day-  $\leq 32$  weeks 0 days gestation, 18-45 years old, who are planning to receive Tdap and IIV during their current pregnancy will be recruited at prenatal clinics whose patients deliver at Duke University Hospital or University of

Cincinnati Medical Center. Pregnant women will be pre-screened for eligibility via medical record review. The study will be introduced to a potential subject by a member of their care team. Potential subjects  $\geq 20$  weeks 0 days gestation will be approached by a member of the research team for study enrollment. Medical and obstetric history, including prior Tdap/Td/TT and influenza vaccine history, will be obtained via participant self-report with verification by chart review whenever feasible (including medical records, employee health records, immunization registry records, and pharmacy records). Study staff will attempt to recruit 10 infants born to women in this study from each site to assess infant pertussis antibody levels prior to 2-month vaccinations. To the extent feasible each site will preferentially recruit 5 infants for each assignment group (simultaneous vs. sequential).

#### 4.4 Reasons for and Handling of Withdrawals

The following may be reason for study withdrawal:

- As deemed necessary by the principal investigator (PI).
- Subject withdrawal of consent.
- Loss to follow-up.
- Termination of the study by the sponsor.

Subjects may withdraw their consent for study participation at any time and for any reason, without penalty. Subjects who withdraw from the study prior to randomization vaccine will be replaced. Subjects who withdraw from the study after receiving vaccine will not be replaced. Every attempt should be made to collect all data specified by the protocol, including collection of pregnancy outcome/safety data via medical record review for subjects who request withdrawal from study interventions/procedures.

#### 4.5 Termination of Study

This study may be terminated for safety concerns of the principal investigators from the Lead or Contributing sites, CDC, or participating IRBs.

## 5 STUDY SCHEDULE, PROCEDURES, & EVALUATIONS

### 5.1 Schedule of events

Pregnant women meeting the proposed eligibility criteria (Section 4.1-4.2) will be recruited. Written informed consent (Appendix I) will be obtained from study participants prior to conducting any study procedures. **Table 2** describes the proposed schedule of study visits with further details below.

Procedure	Screening Visit* Day -28 to 1	Visit 1 Day 1	Visit 2 Day 4 $\pm$ 1	Visit 3 Day 9 + 3	Visit 4 Day 22 + 7	Visit 5 Day 25 – 32 $\pm$ 1	Visit 6 Day 30 – 37 + 3	Visit 7 Day 43 -50 + 7	Visit 8 Delivery	Visit 9 Infant Blood Draw	Unscheduled Visit
Type of contact	Chart Abstraction/ Clinic	Clinic	Phone/ Email/ Text	Phone/ Email/ Text	Clinic	Phone/ Email/ Text	Phone/ Email/ Text	Clinic/ Phone/Email/ Text	Hospital/ Chart Abstraction	Clinic	Clinic
Informed consent & Medical Release of Information	X									X e	
Review Eligibility Criteria	X	X									
Review eligibility criteria for Tdap vaccination					X a						
Data Collection b	X	X	X	X	X	X	X	X	X		X
Influenza and Td/TT/Tdap Vaccination History	X										
Vital signs (temperature, heart rate, respiratory rate and blood pressure) c		X			X a						X

Collection of Cord Blood & Placenta									X		
Randomization		X									
Vaccination		X			X a						
Dispense and review instructions for Memory aid supplies & (REDCap or paper)		X			X						
Complete Memory aid form (REDCap or paper)		X	X	X	X	X	X				
Reactogenicity (local & systemic)			X	X		X	X				
Concomitant medications	X	X	X	X	X	X	X	X	X		X
Obtain solicited & unsolicited adverse events		X	X	X	X	X	X				X
Obtain medically-attended events and serious adverse events		X	X	X	X	X	X	X	X		X
Infant Data Collection d										X	
Infant Blood Sample (DBS)										X	
* Screening visit may occur simultaneously with Visit 1											
a Procedures for subjects in sequential group only											
b Data collection includes demographic information, medical and obstetric history, current pregnancy status. Changes in baseline medical status such as worsening or new onset condition will be capture as adverse events											
c Vital signs measured prior to vaccinations during Visit 1 and Visit 4											
d Data collection includes pertussis-specific medical history											
e Informed consent to be completed prior to Visit 9 blood draw											

**Screening Visit, Study Day -28 to 1 (Chart Abstraction & Clinic Visit – may occur simultaneously with Visit 1)**

- Obtain written informed consent (Appendix I) and release of medical record information
- Review and confirm study eligibility
- Obtain information on preferred method of contact for follow-up (telephone, email or reminder)
- Obtain demographic data
- Obtain month/year of prior history of influenza (IIV or LAIV) vaccines for the past 2 years
- Obtain month/year of any prior history of Tdap
- Obtain month/year of prior history of Td/TT vaccines in the past 10 years
- Obtain medical and obstetric history and current pregnancy status
- Obtain current concomitant medication use

**Visit 1, Study Day 1 (Vaccination Day) - Screening, Enrollment, and Randomization (Clinic Visit)**

- If Screening Visit occurred prior to Visit 1, review and confirm eligibility and all data collected during Screening Visit
- Obtain vital signs including oral temperature prior to vaccination
- Obtain 15mL blood sample prior to vaccination for serologic analysis (Section 6)
- Randomize study participant to simultaneous or sequential vaccine administration (Section 5.2.1)
- Administer assigned study products – Trained, licensed research staff will administer either IIV alone or IIV + Tdap as described in Section 5.2.3. Ensure participants receive corresponding Vaccine Information Sheets (VIS) during visit.
- Dispense memory aid (Appendix B and C), thermometer, and ruler (in order to standardize measurements). Review instructions for use of thermometer, ruler, and

memory aid (Appendix A) completion.

- Confirm preferred method of contact for follow-up (telephone, text or email reminder)
- Confirm date of next scheduled prenatal appointment
- Record any AEs and SAEs during post-vaccination monitoring

**Visit 2, Study Day 4 (window Days 3 – 5) Phone Call/Email/SMS Text Follow-Up**

Study staff will contact study participants (Appendix F) to review the memory aid data and record any adverse events (AEs), serious AEs (SAEs), concomitant medications, and current medical/pregnancy status as described in Section 5.1. Participants will be reminded that they will be contacted again after Day 8.

For participants who choose to utilize REDCap web-based system for entry of memory aid information, study staff will review REDCap system to confirm data capture and assess for any AEs, SAEs, and concomitant medications. Subjects who chose to utilize REDCap will be called if they have not entered their information to remind them to enter their information.

**Visit 3, Study Day 9 (window Days 9 – 12) Phone Call/Email/SMS Text Follow-Up**

Study staff will contact study participants (Appendix F) to review the memory aid data and record any AEs, SAEs, concomitant medications, and current medical/pregnancy status as described in Section 5.1. Participants who are lost to follow-up by phone contact will continue to be called on a weekly basis until approximately Day 45 following vaccination for safety assessment. Study staff will also attempt to follow up with participants at subsequent scheduled prenatal appointments which should be within 2-4 weeks from enrollment visit based on routine prenatal care guidelines.

For participants who choose to utilize REDCAP web-based system for entry of memory aid information, study staff will review REDCAP system to confirm data capture and assess for any AEs, SAEs, and concomitant medications. Participants who are lost to follow-up by phone contact will continue to be called on a weekly basis until approximately Day 45 following vaccination for safety assessment.

**Visit 4, Study Day 22 (window Days 22 – 29) Clinic Visit**

- For study participants in the sequential study group, review exclusion criteria listed in section 4.2 for Tdap vaccination
- Obtain vital signs including oral temperature prior to vaccination for study participants in the sequential group.
- Study staff will review the memory aid data and record any AEs, SAEs, concomitant medications, and current medical/pregnancy status as described in Section 5.1
- Obtain 15mL blood sample for serologic analysis (Section 6). Study participants in sequential group to have blood sample obtained prior to vaccination.
- For subjects in the sequential study group, trained, licensed research staff will administer Tdap as described in Section 5.2.3. Ensure participants receive Tdap Vaccine Information Sheets (VIS) during visit.
- Confirm subjects still have previously dispensed thermometer and ruler; if not, provide new supplies. Review instructions for use of thermometer, ruler, and memory aid (Appendix A) completion. All subjects will complete the memory aid (Appendix D and E) again to allow for the collection of “mock” data in the simultaneous group for comparison with the sequential group. Simultaneous group will only provide information for systemic reactions and oral temperature.

- Confirm preferred method of contact for follow-up (telephone or email reminder)
- Confirm date of next scheduled prenatal appointment

**Visit 5, Study Day 25 - 32 (window Days 24 – 33) Phone Call/Email/SMS Text Follow-Up**

Study staff will contact study participants (Appendix F) to review the memory aid data and record any AEs, SAEs, concomitant medications, and current medical/pregnancy status as described in Section 5.1. Participants will be reminded that they will be contacted again after Day 29. Participants who are lost to follow-up by phone contact will continue to be called on a weekly basis following vaccination until approximately Day 45 for safety assessment. Study staff will also attempt to follow up with participants at subsequent scheduled prenatal appointments which should be within 2-4 weeks from enrollment visit based on routine prenatal care guidelines.

**Visit 6, Study Day 30 - 37 (window Days 30 – 40) Phone Call/Email/SMS Text Follow-Up**

Study staff will contact study participants (Appendix F) to review the memory aid data and record any AEs, SAEs, concomitant medications, and current medical/pregnancy status as described in Section 5.1. Participants who are lost to follow-up by phone contact will continue to be called on a weekly basis until approximately Day 45 following vaccination for safety assessment. Study staff will also approach participants at follow-up prenatal appointments which should be within 2-4 weeks based on routine prenatal care guidelines.

**Visit 7, Study Day 43 - 50 (window Days 43 – 57) Clinic Visit for sequential group, Phone Call/Email/Text for simultaneous group**

- This review will be done by phone call/email/text for study participants (Appendix F) in the simultaneous group and in clinic for participants in the sequential group. Study staff will review the memory aid data and record any AEs, SAEs, concomitant medications, and current medical/pregnancy status as described in Section 5.1. Obtain 15mL blood sample for serologic analysis for sequential group only (Section 6)

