### 3.2 Laboratory studies

**3.2.1 Serologic studies** – We will evaluate pre- and post-vaccination serologic responses in both simultaneous and sequential vaccination groups. A microsphere based multiplex antibody capture assay to determine levels of IgG to pertussis toxin, filamentous hemagglutinin, pertactin, and fimbriae (only for 2016-17 influenza season) in the serum will be performed by the laboratory at the CDC according to CDC protocol MPIR-4301. Tetanus and diphtheria toxoid IgG levels will be measured by an enzyme linked immunoassay (ELISA) at the Duke Human Vaccine Institute ([name] lab). In addition, IgG levels will be measured

for the for the specific viral strains included in the 2016-2017 and 2017-2018 quadrivalent IIV (depending upon vaccine availability) using hemagglutination inhibition assays at the Duke RBL Virology Unit. Venous blood (approximately 15 mL of blood) will be collected from each subject before and 21(+7) days after each vaccination. Additionally, maternal and cord blood (approximately 15mL of blood each) will be collected at delivery for serological analysis in both simultaneous and sequential vaccination groups. An assessment of placental antibody transfer (maternal:cord antibody ratio) will be determined. Prior to the 2-month infant vaccination visit, a blood sample (up to 0.5 mL) will be obtained via heel stick on a subset of 10 infants at each site (20 total). The blood sample will be used to form 5 dried blood spots (DBS) and sent to the CDC lab to determine levels of IgG to pertussis toxin, filamentous hemagglutinin, and pertactin.

- 3.2.2 Placental pathology** – Routine placental pathology includes gross and microscopic evaluation of the placenta (including its weight), umbilical cord (including length, diameter, number of vessels, coiling, and insertion point) and fetal membrane characteristics. Histologic chorioamnionitis is diagnosed using standard hematoxylin and eosin (H & E) staining to identify inflammatory cells (neutrophils, lymphocytes, eosinophils, etc.) as infiltration of the chorionic plate by neutrophils is diagnostic of chorioamnionitis. Chorioamnionitis is staged as per the grading system described in Section 6.4 below.

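### Section 5.1 and Table 2 permit the sequential arm's post-Tdap blood draw on days that Section 3.2.1 does not, because Visits 5 to 7 are not tied to each woman's own Visit 4

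*Combined protocol and SAP*

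**What the plan says.** All references are to the combined protocol and SAP.

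- **Vaccination days.** The simultaneous arm receives both vaccines on Day 1 ("Visit 1, Study Day 1 (Vaccination Day"). Visit 4 is "Study Day 22 (window Days 22 – 29) Clinic Visit", and there "For subjects in the sequential study group, trained, licensed research staff will administer Tdap as described in Section 5.2.3".
- **Blood samples.** Section 3.2.1 ties sampling to vaccination: blood "will be collected from each subject before and 21(+7) days after each vaccination". In 5.1, the simultaneous arm's post-vaccination sample is drawn at Visit 4. The sequential arm's post-Tdap sample is drawn at Visit 7, "Study Day 43 - 50 (window Days 43 – 57) Clinic Visit for sequential group".
- **Contacts between Visits 4 and 7.** Visit 5 is "Study Day 25 - 32 (window Days 24 – 33") and Visit 6 is "Study Day 30 - 37 (window Days 30 – 40"). Both apply to both arms. The Visit 5 text also has staff tell women that the next contact comes after Day 29.
- **Anchoring.** Neither Table 2 nor 5.1 says that a woman's dates for Visits 5 to 7 count from her own Visit 4.
- **Analysis.** Section 7.1.3 presents between-arm comparisons of geometric mean titers (GMTs) and seroprotection proportions with confidence intervals. Regression adjustment is an optional secondary analysis, with BMI and race as the examples; sampling day is not named.

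**The concern.** Visit 4 can fall on any of eight days, but the windows for the visits that follow it are printed once for everyone. The tolerance sits on the whole range instead of on each woman's date. A coordinator working from Table 2 could therefore draw a sample that is in window for the visit schedule and out of window for 3.2.1.

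The sample matters. Maternal immune response is a primary objective, and Section 1.1 gives diminished pertussis antibody after co-administration as a reason for concern. The natural comparison sets the simultaneous arm's Visit 4 sample against the sequential arm's Visit 7 sample. It is cleanest when time since Tdap has the same permitted range in both arms. As printed in 5.1, it does not.

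The same drafting affects the Visit 5 and 6 contacts, which review the memory aid that starts at Visit 4.

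**Working it through.** **Inputs.** Simultaneous arm vaccinated on Day 1 (5.1, Visit 1). Visit 4 on Days 22 to 29; sequential-arm Tdap on that day (5.1, Visit 4). Windows: Visit 5, Days 24 to 33; Visit 6, Days 30 to 40; Visit 7, Days 43 to 57 (5.1). Sampling rule: 21 to 28 days after each vaccination (3.2.1).

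**Step 1: reproduce the printed ranges.** After Visit 1 (Day 1), Table 2 places Visits 2, 3 and 4 on Day 4 ±1, Day 9 +3 and Day 22 +7, which are offsets of +3 ±1, +8 (+3) and +21 (+7). Applying these offsets to a Visit 4 on Day 22 to 29 gives:

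| Visit | Nominal days | Full window | As printed? |
|---|---|---|---|
| 5 | 22+3 to 29+3 = 25 to 32 | 25−1 to 32+1 = 24 to 33 | yes |
| 6 | 22+8 to 29+8 = 30 to 37 | 30 to 37+3 = 40 | yes |
| 7 | 22+21 to 29+21 = 43 to 50 | 43 to 50+7 = 57 | yes |

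So the printed ranges are the outer limits over all women of a schedule counted from Visit 4.

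**Step 2: days from Tdap to the Visit 7 draw, reading 5.1 alone.** Gap = Visit 7 day − Visit 4 day.

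- Shortest: 43 − 29 = 14 days. Longest: 57 − 22 = 35 days.
- Visit 4 on Day 22 allows 43 − 22 = 21 to 57 − 22 = 35 days. Visit 4 on Day 29 allows 14 to 57 − 29 = 28 days. A gap under 21 days therefore needs a Visit 4 later than Day 22.
- Simultaneous arm: 22 − 1 = 21 to 29 − 1 = 28 days.
- Eight Visit 4 days times 15 Visit 7 days gives 120 permitted pairs. Of these, 28 have a gap under 21 days and 28 a gap over 28 days, so 56 conflict with 3.2.1. This counts calendar pairs; it is not an expected frequency.

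**Step 3: centre of the ranges.** (14 + 35)/2 = 24.5 days and (21 + 28)/2 = 24.5 days. The windows differ in width (21 days against 7), not in centre.

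**Step 4: Visits 5 and 6 relative to Visit 4.**

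- Visit 5: 24 − 29 = −5 to 33 − 22 = +11 days, so a contact can precede Visit 4.
- Visit 6: 30 − 29 = +1 to 40 − 22 = +18 days. At +1 the woman is on diary Day 2 of 8. The matching Visit 3 falls 9 − 1 = 8 to 12 − 1 = 11 days after Visit 1.
- Day 29 is diary Day 8 only for a Day 22 Visit 4 (22 + 7 = 29). For a Day 29 Visit 4, diary Day 8 is Day 36 (29 + 7).

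**Step 5: after anchoring.** Visit 7 at Visit 4 + 21 (+7) gives 21 to 28 days after Tdap, the same as the simultaneous arm and as 3.2.1.

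**Step 6: a neighbouring mismatch.** Section 5.2.3 places Tdap 22 to 29 days after IIV. Visit 4 on Days 22 to 29 is 21 to 28 days after Day 1. Taken literally, 5.2.3 puts Tdap on Days 23 to 30, and the Step 2 range becomes 43 − 30 = 13 to 57 − 23 = 34 days.

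**The case against.** The strongest reply is that sampling is already anchored. Section 3.2.1 applies to every draw, so a site that respects both sections can sample only at 21 to 28 days after Tdap, as in the simultaneous arm. Step 1 also shows what the authors meant, and a Visit 5 held before Visit 4 is not a realistic reading. This stands in part. The intent is clear, and 14 to 35 days describes 5.1 read without 3.2.1, not the protocol as a whole. It does not remove the conflict: Table 2 and 5.1 are the operational schedule, and they mark as in window draws that 3.2.1 rules out.

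Two stronger readings are tempting, and the documents support neither.

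- **A reader might infer that the GMT comparison is biased in a known direction, or by a calculable amount.** The two ranges share a midpoint, so the windows alone imply extra spread. A shift in mean sampling time would need uneven scheduling, which nothing in the plan implies. No antibody kinetics are given, so no percentage effect can be attached.
- **A reader might infer that reactions after Tdap are undercounted in the sequential arm.** The diary runs Days 1 to 8 from the visit itself, whatever the date of the call (5.3, Appendices A, D and E). It is reviewed again at Visit 7 (5.1, 5.3, Appendix F), which even on the literal reading is at least 14 days after Visit 4. The Visit 5 and 6 windows also apply to the simultaneous arm's mock systemic diary. An early contact may find the diary incomplete, but no loss of data and no one-arm effect is shown.

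It is also fair to say that this is a descriptive pilot of about 80 women, not powered for group comparisons.

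**Conclusion.** The inconsistency is real and should be corrected. Table 2 and 5.1 contradict 3.2.1 on when the sequential arm's post-Tdap sample may be drawn: 14 to 35 days against 21 to 28. The consequence supported by the documents is avoidable extra timing variation in one arm of a primary-objective comparison that names no adjustment for sampling day. Its effect on the GMT comparison cannot be given a direction or a size.

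For Visits 5 and 6, the windows allow mistimed contacts, and the Day 29 reminder is right for only one of the eight possible Visit 4 days. That is a matter of wording and workflow.

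These conclusions assume that Tdap is given within the printed Visit 4 window and that sites apply the 5.1 windows as written. The day arithmetic is certain. How often a draw would fall outside 21 to 28 days is unknown.

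**What to change.** 1. In Table 2 and 5.1, state that Visits 5, 6 and 7 count from the woman's actual Visit 4 date: +3 (±1), +8 (+3) and +21 (+7) days. Keep the printed study-day ranges, if at all, only as the outer limits across women. This brings the schedule into line with 3.2.1.
2. Reword the Visit 5 reminder so that it refers to the end of the woman's own post-Visit 4 diary instead of Day 29.
3. Report days since Tdap for every post-Tdap sample, by arm. Administration date and time (5.2.3) and collection date and time (5.5.1) are already recorded, so nothing new is collected.
4. Reconcile the interval in 5.2.3 with the Visit 4 window in 5.1. This review takes no position on which should stand.

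**Cost.** Wording changes and one added line of reporting, with no extra visits or samples. Scheduling of Visit 7 becomes slightly tighter: each sequential woman has 8 eligible days (28 − 21 + 1) instead of the 15 that 5.1 prints (57 − 43 + 1).

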**Visit 8, Delivery Visit, Medical Record Review/Phone Call/Hospital**

Study staff will screen the inpatient census for the site-specific Labor & Delivery/Birthing Centers daily to identify study participants admitted for delivery. Electronic medical records will be comprehensively reviewed for detailed information about maternal health events during pregnancy and maternal and infant outcomes as defined by the American College of Obstetrics & Gynecology's REVITALIZE Obstetric Data Definitions. Concomitant medications during delivery hospitalization will be limited to those that are relevant to pregnancy outcomes of interest, e.g. antenatal corticosteroids, or tocolytics in the setting of preterm labor/preterm birth, magnesium in the setting of preeclampsia, antibiotics in the setting of Group Beta Streptococcus (GBS) prophylaxis or chorioamnionitis, etc. Maternal blood and infant cord blood will be collected at this visit. Placentas will be sent for clinical pathology examination.

In order to capture and follow all participants, as a separate plan of follow up, study participants who are not identified via medical record review at delivery will be contacted by phone approximately 2 weeks after their estimated due date to determine if delivery

occurred elsewhere. If so, maternal and infant medical records will be requested from the delivery hospital for data collection.

### ***Visit 9, Infant Follow up Clinic Visit***

At Visit 9, infants must be  $\geq 6$  weeks and  $\leq 12$  weeks of age and not have received any dose of DTaP. Study staff will obtain a blood sample via heel stick (up to 0.5 mL) prior to the infant receiving 2-month vaccination series to collect 5 dried blood spots (DBS). Study staff will recruit 10 infants born to women in this study from each site and will attempt to preferentially recruit 5 infants for each assignment group (simultaneous vs. sequential) at each site. Dried blood spot cards will be sent to the CDC for testing.

Additionally, study staff will collect information about pertussis symptoms, diagnosis and exposure in the infants. The study staff will also assess to ensure the child does not have an increased risk for bleeding or infection after a heel stick.

